3.1 Study Design Overview

We are proposing a mixed-method study with three research aims that uses rigorous, systematic steps (see Figure 2). For Aim 1, we will recruit 260 YLMSM to assess HPV knowledge, awareness, health beliefs, attitudes toward the HPV vaccine, healthcare experiences, behaviors, and among those unvaccinated, intentions to receive the HPV vaccination, HPV vaccine education learning preferences, social media use, health literacy, sociodemographic characteristics, among others. For Aim 2, we will interview 20 key stakeholders to inform intervention content and delivery methods as well as to identify potential implementation facilitators and barriers and receive feedback on the intervention. In Aim 3, informed by PHM and HBM and the data collected in Aim 2, we will adapt and update the Cancer 101 HPV module to develop an educational intervention in Spanish targeted for YLMSM. Finally, we will receive feedback on the educational intervention (e.g., content, aesthetics, appeal, modality, format) from 24 YLMSM in PR (up to n=12) and FL (up to n=12) via focus groups or individual interviews.

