Inclusion criteria for Aims 1 and 3 will include self-identification as: (1) having had sex with a man and/or being attracted to men; (2) Hispanic/Latino ethnicity; (3) able to read, write, and understand Spanish (for Aim 1) and Spanish or English (for Aim 3); (4) aged 18-26 years; (5) primary residence in either FL or PR. An additional eligibility criterion for Aim 1 is having access to the internet (to complete the online survey). Additional eligibility criteria for Aim 3 are having either regular access to a working telephone or being able to attend an in-person focus group (modifications related to COVID-19 situation will allow virtual modality to complete the focus groups or individual interviews). Exclusion criteria for Aims 1 and 3 will include self-identification as: (1) transman or transwoman or (2) aged <18 years or ≥27 years. Individuals who contact the research team about interest in participating on Aims 1 or 3 can be directed to Aims 1 or 3 for possible recruitment. Individuals can participate in more than 1 aim, but not more than one time in a single aim.

3.2.c. Aim 1 Procedures

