Cultural adaptation of the Cancer 101 HPV module will be informed by data results from Aims 2 and CAB members, and it will be guided by TPB and HBM theories. Individuals interested in participating in Aim 3 will be asked to contact the study team who will assess eligibility. Following development of an initial draft of the educational materials in English and Spanish, using a semi-structured interview guide (see Aim 3 Semi-structured Interview Guide) and established procedures, we will conduct Spanish and/or English-language focus groups and/or individual interviews with 24 YLMSM (12 in each site) to obtain feedback on the intervention. Focus groups or individual interviews will be conducted in-person or remotely (e.g., Zoom, phone) by trained study staff. Focus groups or individual interviews will be conducted in-person or remotely (e.g., Zoom, phone) by trained study staff. Focus groups or individual interviews may be conducted in Spanish or English, depending upon participant preference. Participants will be asked to complete a brief sociodemographics survey (examples include: age, race, employment status) either online (for those participating remotely) or with a pen-and-paper version (for those

participating in person). During the interview and guided by a semi-structured interview guide, participants will be shown examples of platforms and prototypes of materials to solicit their feedback and preferences. Examples include PowerPoint Presentation, Brochure, YouTube and TikTok videos of HPV-related content. We expect that Aim 3 findings will: (1) provide feedback on the acceptability, accessibility, content, and aesthetics of the intervention to be iteratively adapted based upon participant feedback; and (2) identify the preferred dissemination/learning platform(s) and format(s) to deliver the adapted intervention to YLMSM. Focus groups or individual interviews will be audio digitally recorded. Focus groups or individual interviews are anticipated to last between 90-120 minutes. Interviews will be transcribed verbatim. Participants will receive a \$50 gift card. At the end of the interviews, participants will indicate whether they are interested in participating in other parts of the study (e.g., Aim 1).

3.2.i. Assessment of Study Related Variables in Aim 1

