Validated scales used in prior studies (e.g., BRFSS, HINTS) will be included for assessment: sociodemographics (location [PR or FL], age, sexual orientation, gender identification, relationship status, race/ethnicity, household income, health insurance status, employment status, education; Hispanic/Latino-specific cultural items; health literacy; numeracy; prior health behaviors and health care experiences; HPV and HPV vaccine awareness/knowledge; HBM constructs; TPB constructs, information sources/trust in information sources; educational preferences; vaccine receipt preferences; vaccine behaviors; vaccine intentions (among those unvaccinated); comfort with sexual health; sexual experiences & social media use, among others (see Aim 1 Quantitative Survey).

3.2.j. Statistical Considerations

3.2.j.i. Data Analysis

For Aim 1, standard descriptive statistics (e.g., frequencies, proportions, means, standard deviations) will summarize all variables and provide excellent estimates of population parameters. The dependent variables are HPV vaccination status and HPV vaccine intentions. The factors to be evaluated for potential associations will be: sociodemographic characteristics, sexual practices, sexual orientation disclosure, social media preferences, vaccination history, among others. Covariation among variables, including predictors of intentions, will also be estimated, using measures appropriate for the paired variables (e.g., r, beta, odds ratio). For Aims 2 and 3, thematic-content analysis techniques using the principles of Grounded Theory will be performed^{47,48} whereby themes from the focus group transcripts and key stakeholder interviews are identified.

3.2.j.ii. Sample Size/Power Calculations

The overarching goal of Aim 1 is to generate excellent parameter estimates for the design of subsequent research proposals. With a precision of 0.05 and an 80% of statistical power, we estimate a total of n=260 participants, both estimates of single variable means or proportions and the relationships among predictors and outcome variables will have relatively small 95% confidence intervals. If data collection yields complete and high-quality data, a sample size of n=227 is required to achieve 80% power with a 0.05 precision.

3.2.j.iii. Data Management

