3.3 Future Plans

3.3.a. Future Directions/Summary

Guided by health behavior theories and applying systematic and rigorous methods, the proposed innovative study seeks to address multiple cancer disparities through the development of a salient HPV vaccine educational intervention targeted to YLMSM. The culturally-adapted intervention will be tested in a future multi-site randomized controlled trial among YLMSM in FL and PR. Ultimately, this line of research has a significant potential to reduce cancer morbidity and mortality and improve public health.

4. Human Subjects Considerations

4.1.a. Human Subjects Involvement and Characteristics

Procedures for Aim 1:

We will recruit a total of 260 YLMSM in PR and FL using multiple strategies, including in-person recruitment in community settings and at community clinic or community organization locations, social media and dating applications advertisements in Spanish, on platforms such as Instagram®, Snapchat®, and Grindr®, broadcasting media, recruitment flyers in the community, and email invitation to participants from prior studies who have indicated interest in taking part in future studies. CAB members may also assist with recruitment efforts by sharing recruitment materials in various means (e.g., social media platforms, websites, etc.). Individuals who contact the research team about interest in participating on Aims 1 or 3 can be directed to Aims 1 or 3 for possible recruitment when

they indicate that they are interested in participating in other parts of the study. Individuals can participate in more than 1 aim, but not more than one time in a single aim.

For Aim 1 Participants:

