For Aim 1, 260 participants will be enrolled. To be eligible participants must self-identify as: (1) having had sex with a man and/or being attracted to men; (2) Hispanic/Latino ethnicity; (3) able to read, write, and understand Spanish; (4) aged 18-26 years; (5) primary residence in either FL or PR; and (6) having internet access (either via personal device or research team tablet). Exclusion criteria for the online survey will include self-identification as: (1) transman or transwoman, and (2) aged >26 years, 364 days. For the online survey, we will recruit participants with the help of CAB members through the dissemination of recruitment materials (e.g., flyers, social media posts, emails, messages), in-person recruitment in community clinics and/or community organization locations, virtual events (e.g. virtual cancer education events), and by using social media, broadcasting media, and online dating applications advertisements in Spanish. In addition, Aim 1 study flyers may be disseminated in physical spaces, via social media, via presentations, and via email, among other dissemination methods by our team, other Moffitt and PHSU teams/departments/cores, and groups, organizations, and networks in the community. Participants may contact the study team from the contact information or QR code linked to the study lab email address for more information, eligibility inquiry, and for the online survey link. For in-person recruitment, participants will be provided with an information sheet and a QR code that will be clipped to the information sheet. They will be able to complete the survey by scanning the QR code on their own device, or with assistance of a research team member who can scan the QR code on an iPad. The QR code will re-direct participants to the survey. After completing eligibility screening in Spanish via a web-based platform (i.e., Qualtrics, a HIPAA-compliant system), eligible participants will be presented with study information in Spanish, asked to provide informed consent electronically, and complete a Re-CAPTCHA task prior to start of the survey. Consenting participants will complete a survey in Spanish requiring approximately 30 minutes. The survey will be able to be completed on various devices with internet capabilities, including desktop computers, laptops, tablets, and mobile phones. The survey will be programmed and maintained by the Moffitt Participant Research, Interventions, and Measurement (PRISM) Core. PRISM will collect IP addresses as well as GeoLocation Coordinates and may enable additional available settings to identify and prevent multiple null survey submissions that may affect data integrity.

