We will conduct focus groups or individual interviews (i.e., approximately 2-3 in FL and 2-3 in PR) with 24 YLMSM in Spanish and English. Participants will be recruited via Spanish and English flyers at community partner locations, community locations, and community events in PR and FL (e.g., PRIDE events), broadcasting media, online ads (e.g., on social media platforms commonly-used by YLMSM), disseminated in physical spaces, via social media, via presentations, and via email, among other dissemination methods by our team, other Moffitt and PHSU teams/departments/cores, and groups, organizations, and networks in the community, and/or ResearchMatch. For ResearchMatch recruitment, our study will be registered on ResearchMatch.org. The research team will then send our IRB-approved initial recruitment message to potential matches who will have the option of replying “yes,” “no”, or providing no response. The study’s home page in ResearchMatch will provide information about volunteers who have responded “yes.” After the volunteer has authorized ResearchMatch to provide their contact information to the study team, the study team will contact the participant about potential participation, assess eligibility, explain the study, and informed consent through encrypted email, phone call, or a mailed letter. Focus groups or individual interviews will be conducted in-person or remotely (e.g., Zoom, phone) by trained study staff in either English or Spanish, depending upon

participant preference. A brief sociodemographic online or in-person survey will be completed by Aim 3 participants prior to the focus group or individual interview. Individuals who contact the research team about interest in participating on Aims 1 or 3 (when recruitment cap has been completed for that aim) can be directed to Aims 1 or 3 for possible recruitment. Individuals can participate in more than one aim, but not more than one time in a single aim.

For Aim 3 Participants:

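### Aim 3 participants are invited into the Aim 1 survey after seeing HPV materials, with no order, exclusion or flag in the available text; at most 24 of 260 respondents, so the likely effect is small

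*Combined protocol and SAP*

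**What the plan says.** Section 3.2.h describes Aim 3 sessions of 90 to 120 minutes in which "participants will be shown examples of platforms and prototypes of materials to solicit their feedback and preferences". The examples include a slide presentation, a brochure and HPV-related videos. The same section then states: "At the end of the interviews, participants will indicate whether they are interested in participating in other parts of the study (e.g., Aim 1").

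Three other places bear on the route into Aim 1:

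- Section 3.2.b sets the overlap rule: "Individuals can participate in more than 1 aim, but not more than one time in a single aim".
- Section 4.1.a, Procedures for Aim 1, says that people who contact the team "can be directed to Aims 1 or 3 for possible recruitment when" they state an interest in other parts of the study.
- Section 4.1.a, Procedures for Aim 3, ties redirection to a full aim: "when recruitment cap has been completed for that aim) can be directed to Aims 1 or 3 for possible recruitment".

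The Aim 1 exclusions do not mention Aim 3: "Exclusion criteria for the online survey will include self-identification as: (1) transman or transwoman, and (2) aged >26 years, 364 days". Section 3.2.j.i names the outcomes: "The dependent variables are HPV vaccination status and HPV vaccine intentions". It lists no prior-exposure variable and no sensitivity analysis. The removals in section 3.2.j.iii concern fraud and data quality only.

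**The concern.** Aim 1 is a cross-sectional survey intended to find knowledge gaps and learning preferences and to supply parameter estimates for later research. A person who enters it after an Aim 3 session answers the knowledge, belief, educational-preference and intention items just after seeing and discussing HPV materials. Knowledge could then be overstated and the gaps understated, and format preferences could reflect the prototypes shown.

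Of the two dependent variables, vaccination status is mostly past behaviour and would be little affected. Intentions could be affected, but only among the unvaccinated, who are the only people asked.

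The number of crossovers may also stay unknown. Contact details are collected in a separate survey (3.2.c) and the analysis data are de-identified (3.2.j.iii).

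**Working it through.** **The plan's own figure.** The point does not rest on the sample-size calculation. That calculation cannot be strictly rebuilt, because section 3.2.j.ii gives no expected proportion or SD. With a margin of 0.05 at 95% confidence, n = 1.96² × p(1 − p) / 0.05² gives 385 at p = 0.5, and 257 at p = 0.212 (the national rate in the background, which the plan does not link to its calculation). I found no variant that gives 227. Below, 260 and 227 are taken as stated.

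**Is the order possible?** The adaptation draws on Aim 2 and the advisory board (3.2.h), so Aim 3 need not wait for Aim 1. The closing question has practical effect only if Aim 1 may still be open. Section 3.2.c foresees a recruitment booster for Aim 1, so it could well be.

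**Inputs.** Aim 1: N = 260, capped in 3.2.c. Aim 3: k = 24 at most, up to 12 per site (3.1; section 4.1.a says approximately 24). The crossover counts of 6 and 12, and all effect sizes, are assumptions.

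**Share exposed.** k/N: 24/260 = 9.2%; 12/260 = 4.6%; 6/260 = 2.3%.

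**Shift in a mean such as knowledge.** Shift = (k/N) × gain among the exposed. Standard error of the mean = 1/√260 = 0.0620 SD. Gain needed to move the mean by one standard error = 0.0620 × 260/k.

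| Crossovers | Shift for a gain of 0–1.0 SD | In standard errors | Gain needed for a 1-SE shift |
|---|---|---|---|
| 24 | 0–0.092 SD | 0–1.49 | 0.67 SD |
| 12 | 0–0.046 SD | 0–0.74 | 1.34 SD |
| 6 | 0–0.023 SD | 0–0.37 | 2.69 SD |

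The sessions seek feedback rather than teach, so a gain near zero is plausible.

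**Intentions.** Assume 21.2% are vaccinated. The unvaccinated then number 260 × 0.788 ≈ 205, and the exposed share is at most 24/205 = 11.7%. Assume intention rises by 10 to 50 percentage points among the exposed. The bias is then 1.2 to 5.9 points if all 24 are unvaccinated and join, 0.6 to 2.9 points with 12, and 0.3 to 1.5 points with 6. At the 13.7% rate that the background gives for young MSM, the unvaccinated number about 224 and the ceiling share is 10.7%.

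**Why 24 is a ceiling.** Aim 1 requires Spanish literacy while Aim 3 accepts English; a slot must be open under the 260 cap; and anyone who came to Aim 3 from Aim 1 cannot repeat the survey. Redirection because an aim is full may mostly involve people who have seen no materials.

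**Cost of setting people aside.** 260 − 24 = 236, and 236 − 227 = 9. The 95% half-width at p = 0.5 goes from 1.96 × √(0.25/260) = 6.1 points to 1.96 × √(0.25/236) = 6.4 points.

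**The case against.** - **Unseen material.** Section 3.1 describes "rigorous, systematic steps (see Figure 2"), and section 3.2.i refers to the Aim 1 questionnaire. Either could contain a sequence or an exposure item. This stands: the gap is in the available text only.
- **Implied order and tracking.** Section 4.4 says survey-type results will inform the intervention content, which suggests that Aim 1 comes first. Sections 3.2.j.iii and 4.2.b mention study-flow data and tracking documents, and the once-per-aim rule presupposes some tracking. None of this requires Aim 1 to close before Aim 3 starts, and none of it puts an exposure variable into the de-identified survey data.
- **No material effect shown.** The closing question records interest only, and 6 to 12 crossovers cannot move the knowledge mean by one standard error even at the top of the assumed range. This stands and is why the point is minor.
- **Background exposure is accepted anyway.** The plan recruits from prior studies (3.2.a) and at cancer education events (3.2.c), and no criterion requires respondents to be new to HPV education. That is true, but exposure created by the study itself is easier to avoid.
- **The remedy has costs.** Setting aside 24 people uses 24 of the plan's margin of 260 − 227 = 33 (73%) and leaves room for 9/236 = 3.8% in data-quality removals. With about 12 Aim 3 participants per site, a flag combined with age and location also makes small cells in a survey on sexual experience. Both cautions stand. The first applies only if people already enrolled are removed without replacement.

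**Conclusion.** The concern holds as a minor design weakness. The plan describes a route from exposure to HPV materials into the survey meant to measure HPV knowledge, preferences and intentions, and the available text neither closes that route nor records its use.

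The size is bounded by 24 of 260 (9.2%) and is probably much smaller, possibly nil. For knowledge, the worst case under the assumed gain of up to 1.0 SD is 0.09 SD, or 1.5 standard errors; with 6 to 12 crossovers it stays below one standard error. For intentions, the extreme case (all 24 unvaccinated, all joining, a 50-point rise) reaches 5.9 points, above the plan's 0.05 precision, while partial uptake gives far less. The effect sizes are assumptions. Nothing here shows that the Aim 1 estimates are in fact biased.

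**What to change.** 1. In 3.2.h, remove Aim 1 as the example in the closing question.
2. In the redirection text of 3.2.b and 4.1.a, add: *People who have attended an Aim 3 session are not directed to Aim 1.* Movement from Aim 1 to Aim 3 stays allowed, since it does not affect the survey answers.
3. Add one Aim 1 screener item: *Have you already attended an Aim 3 focus group or interview?* Carry the answer into the analysis data at least as a flag. The team may use it as an exclusion instead.
4. In 3.2.j.i, state that Aim 1 estimates are reported with and without flagged respondents. Do not tabulate the flag by site and age, given the small numbers.

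For people already enrolled, do this where records can be linked; otherwise report the possible number as a limitation. If Figure 2 or the questionnaire already settles the matter, citing it in 3.2.b is enough.

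The cost is one screener item and a short amendment. A flag leaves eligibility unchanged. An exclusion at screening uses none of the 260 slots, because screening precedes consent and the survey. The change does not address exposure from outside the study.

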Recruitment of Seeds: Instances where the recruitment needs a booster to achieve the sample goal of 260 participants for Aim 1, we will conduct a respondent driven sampling approach. When each eligible participant is able to identify up to three peers with the study characteristics. HPV project team will recruit an initial group of approximately 10-15 seeds. The number of initial seeds will depend on the capacity of the project team as well as the locations and community partners population scope. The eligibility criteria for the seeds will be the same for aim 1. When a potential seed is identified or contacted thru the HPV team or Community-Based or Clinic Partner, HPV project team will briefly describe the current HPV Survey and ask the potential seed if he would be willing to share with peers a study coupon to invite them to the study. If the potential seed do so at that time, he will be given a referral card to provide to their peers who has the eligibility criteria (a recruitment coupon may also serve as a referral card for seeds, see Appendix A). The referral card (coupon) will have: 1) QR code to access the survey, 2) ID Number, 3) general information about the study.

Eligibility Criteria for Valid Seeds: Once eligible seeds agreed they would be willing to recruit other participants for a small incentive. After a brief training on the recruitment process, those who agree to recruit will be given up to 3 coded, non-replicable coupons (Appendix A). The participant will be told to give one coupon to each of up to 3 individuals he knows and has seen in the past 30 days who live in the project area and meet certain specific criteria. Each coupon will have the current HPV logo, location(s) of field site locations, phone number(s) where staff can be reached in case of any question or concern, and a Survey ID number printed on it. The Survey ID on the coupon will be linked

to (but not identical to) the Survey ID of the participant the coupon is issued to (i.e., the recruiter), which will be documented in the coupon manager log (Appendix B).

Coupon Redemption: All persons who bring a valid coupon will scan QR code for eligibility. Those found to be eligible and who give consent to participate in the survey. After completion of the survey, the HPV team will identify the valid seed entries to provide the small incentive (\$5.00 per valid seed recruited) and send through electronic gift card to the recruiter.

3.2.d. Aim 2 Participant Recruitment

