MCC and PHSU will complete a data sharing agreement to safely share the database for secondary analysis. The data sharing agreement will include all the HIPAA requirements. A data entry system, designed by the PRISM Core, will store and manage study flow information and questionnaire data. Data will be stored on password-protected computers on the secure MCC and PHSU network servers. Study documents will be secured in locked filing cabinets. Following data cleaning, de-identified data will be sent electronically to [name] who will convert the Excel file into SAS (SAS Institute, Inc., Cary, NC) to conduct data analyses. Drs. [name], [name] (MPIs), and [name] (Co-I; biostatistician) the staff statistician will meet regularly to discuss Aim 1 data processing and analyses. NVivo® transcription will be used to transcribe all audio files according to HIPAA requirements. For Aims 2 and 3, all transcriptions will be submitted to review process for accuracy.⁴⁹ All qualitative data will be gathered, organized, and managed using NVivo®.

To ensure integrity of responses in the survey in Aim 1, a multi-step approach informed by recommendations in the literature will be conducted. This includes the addition of re-CAPTCHA tasks⁵⁰ and/or attention checks throughout the survey.⁵¹ To verify the validity of the data post-survey, staff members (including PRISM and study staff) will check IP addresses to identify duplicates, assess response times to identify fast respondents, identify consecutive responses using a straight lining method, and check the quality of open-ended survey responses. Participants will be removed from the study without compensation if the research team finds evidence of fraudulent responses. Respondents who fail these checks will be removed from the final analytic sample.

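### If the Aim 1 coupon booster is used, the planned 95% intervals take no account of recruitment chains and would probably be too narrow: slightly after one wave, more if recruits also recruit

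*Combined protocol and SAP*

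**What the plan says.** Section 3.2.c (Recruitment of Seeds) makes the booster conditional. It applies in "Instances where the recruitment needs a booster to achieve the sample goal of 260 participants for Aim 1" and starts with roughly 10-15 seeds. After a short training, "those who agree to recruit will be given up to 3 coded, non-replicable coupons", one for each of up to three people "he knows and has seen in the past 30 days".

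The number of waves is not stated, and the text points both ways. The opening, "When each eligible participant is able to identify up to three peers with the study characteristics", reads as if every participant may recruit. The training and coupon steps are described only for seeds.

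The link between recruit and recruiter is to be kept. Each coupon's ID is tied to "the Survey ID of the participant the coupon is issued to (i.e., the recruiter), which will be documented in the coupon manager log". The only use given for the link is paying the recruiter $5 per valid recruit.

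On analysis, section 3.2.j.i says ordinary descriptive statistics "will summarize all variables and provide excellent estimates of population parameters", with r, beta or odds ratios for associations. Section 3.2.j.ii adds that "estimates of single variable means or proportions and the relationships among predictors and outcome variables will have relatively small 95% confidence intervals". Section 3.2.j.iii says that after cleaning "de-identified data will be sent electronically" for analysis, and does not say whether coupon or recruiter IDs go with them. None of these sections mentions clustering, a design effect or a chain-aware estimator.

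**The concern.** Men who know each other and met within the last month are likely to share clinics, information sources and norms. The study's own framework (section 2.4) includes subjective norms. Vaccination status and intention are the two dependent variables, and both are plausibly alike within a chain. A positive correlation means that each coupon recruit adds less information than an independent respondent. A standard error computed as if all were independent is then too small.

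Aim 1 exists to supply parameter estimates for later proposals. If coupons are used and the links are ignored, a reader of those estimates cannot tell how much precision is overstated. The wave question matters because correlation builds up along longer chains: with one wave the loss is small, and with two it can be moderate.

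**Working it through.** **The plan's own figure.** Section 3.2.j.ii gives n=260 (227 with complete data) at a precision of 0.05 and 80% power, but no proportion, standard deviation or effect size. The figure therefore cannot be reproduced uniquely. The nearest match is the 95% precision formula with the 21.2% national vaccination rate from the opening background text: 1.96² × 0.212 × 0.788 / 0.05² = 257. That formula assumes independent respondents, that is, a design effect of 1.

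**Inputs from the documents.** n = 260; 10-15 seeds; up to 3 coupons per recruiter; 23.7% vaccinated (males in Puerto Rico, background text) as an example proportion.

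**Assumed inputs.** Correlation L per referral link of 0.1-0.3, the redemption rate, and seeds counted within the 260.

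**Method.**
- The correlation between two men in one tree is L raised to the number of links between them.
- Tree design effect: DE = (sum of L^distance over all ordered pairs, each man with himself included) / tree size.
- Variance inflation for the whole sample: f = 1 + (m/260)(DE − 1), where m is seeds plus recruits.
- Effective n = 260/f. The correct interval is √f times as wide. Coverage of a nominal 95% interval is 2Φ(1.96/√f) − 1.

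**Example: one wave, all three coupons redeemed (tree of 4).** There are three pairs one link apart and three pairs two links apart.
- L = 0.1: DE = [4 + 2(3 × 0.1 + 3 × 0.01)]/4 = 1.165. With 10 seeds, m = 40, f = 1 + (40/260)(0.165) = 1.025 and effective n = 254.
- L = 0.3: DE = [4 + 2(3 × 0.3 + 3 × 0.09)]/4 = 1.585. With 15 seeds, m = 60, f = 1 + (60/260)(0.585) = 1.135 and effective n = 229.

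**All scenarios** (each range runs from 10 seeds, L = 0.1, to 15 seeds, L = 0.3):

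| Scenario | DE | Coupon recruits | f | Effective n | Extra width needed | Coverage |
|---|---|---|---|---|---|---|
| Booster unused | 1 | 0 | 1 | 260 | 0% | 95% |
| One wave, 3 redeemed | 1.165-1.585 | 30-45 (12%-17%) | 1.025-1.135 | 254-229 | 1%-7% | 95%-93% |
| Two waves, 1 redeemed | 1.140-1.460 | 20-30 (8%-12%) | 1.016-1.080 | 256-241 | 1%-4% | 95%-94% |
| Two waves, 2 redeemed | 1.193-1.734 | 60-90 (23%-35%) | 1.052-1.297 | 247-200 | 3%-14% | 94%-91% |
| Two waves, 3 redeemed | 1.220-1.953 | 120-180 (46%-69%) | 1.110-1.715 | 234-152 | 5%-31% | 94%-87% |

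**In percentage points.** At 23.7% the half-width under independence is 1.96 × √(0.237 × 0.763/260) = 5.17 points. Multiplied by √f, it becomes 5.2-5.5 after one full wave, 5.3-5.9 after two waves with two redeemed, and 5.4-6.8 at the extreme.

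**Associations.** For a regression slope, the per-link term is the product of the predictor and residual correlations. If each is 0.2-0.3, the product is 0.04-0.09. Two waves with two redeemed then give f = 1.019-1.069 (1%-3% wider), and two full waves give 1.040-1.146 (2%-7% wider).

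**Does clustering on the seed work with so few trees?** This was simulated for two full waves: 8,000 samples per setting, p = 0.237, n = 260, each recruit copying his recruiter's status with probability L. Coverage was 85.5%-92.3% unclustered, 92.8%-93.7% clustered without correction, and 94.3%-94.9% with CR2 variance and Satterthwaite degrees of freedom (25-36). About one point of the unclustered shortfall is not due to coupons: the exact coverage of the usual Wald interval with independent data at this p and n is already 94.1%.

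**The case against.** The booster is a fallback. Social media, dating applications, broadcast media, clinics, flyers, email lists and events are the main routes, and if they fill the sample nothing here applies. Coupon issue is described in detail only for seeds. Under that reading the correct intervals are at most about 7% wider, and with one coupon redeemed per seed the effective n is 251-258. Intervals would still be relatively small, as the plan says. The methods are listed as examples, a biostatistician is on the team, and the recruiter link is recorded, so clustering could be added later. Treating recruits as independent is inferred from silence.

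Most of this stands, and it sets the priority low. It does not remove the point. Nothing limits the booster to one wave, and a later adjustment is possible only if the IDs reach the analyst, which the plan does not promise.

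Three stronger readings are not supported:
- A reader might infer that the intervals will certainly be too narrow, or that coverage near 87% is to be expected. The documents give no correlation, and that figure needs every coupon redeemed over two waves, at the top of the assumed range, with up to 69% of the sample recruited by coupon. Equal correlation throughout a tree would give larger losses (effective n 200-70 for two full waves, correlation 0.05-0.30), but nothing in the documents favours that model.
- A reader might infer that without coupons the intervals are sound. That does not follow. Men recruited at the same clinic or event may also be alike, and this is a convenience sample, so selection limits population estimates in a way that clustering does not cure.
- A reader might infer from Appendix B that recruit IDs are not logged. The extracted Spanish template is only a header row and the English one is missing, while section 3.2.c says the link is documented there.

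**Conclusion.** The concern holds as a conditional statement of low priority. If coupons are used, the plan as written makes no allowance for recruitment chains. With the positive correlation that is expected, its 95% intervals for proportions and means would be too narrow. The shortfall is about 1%-7% in width after one full wave, 3%-14% after two waves with two coupons redeemed, and 5%-31% at the upper extreme. Associations are affected less. These sizes rest on the assumed 0.1-0.3 correlation per link, its decay with distance, and the assumed redemption. The direction rests on the correlation being positive. If the booster is unused, this particular problem does not arise.

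**What to change.** In section 3.2.j.i, state that if coupons are used:
- the recruit, recruiter and originating seed IDs stay in the de-identified analysis file;
- Aim 1 intervals and regressions use standard errors clustered on the originating seed, each non-coupon participant being his own cluster, with a small-sample correction such as CR2 with Satterthwaite degrees of freedom;
- the share recruited by coupon is reported.

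In section 3.2.c, state whether coupon recruits may themselves recruit. A one-wave cap is optional. It keeps the loss small but limits the booster to about 30-45 men unless seeds are added.

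The cost is one analysis option and possibly one or two extra log fields. If there is in fact no correlation, intervals widen by about 1% after one full wave (t on 153 degrees of freedom/1.96 = 1.01) and by up to about 5% after two (25 degrees of freedom, 1.05). If the booster is not used, nothing changes.
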